Characteristics of an Adverse or Serious Adverse Event	22
Relationship to Study Intervention	22
Expectedness	22
Severity	22
Reporting Procedures	22
Protocol Deviations and Other Unanticipated Problem Reporting	23
Privacy	23
12. Data management	24
13. Data & Safety Monitoring Plan	25
Plans for Assurance of Compliance regarding Adverse Event Reporting.	25
Plans for Assuring Data Accuracy and Protocol Compliance.	25
Data Safety Monitoring Board (DSMB).	25
Quality Assurance and Confidentiality	26
Confidentiality	26
14. Privacy, Data Storage & Confidentiality – see Research Data Security Plan.	26
15. IRB of Record	26
Appendix 1: Schedule of Events	30
Appendix 2: Study Workflow	310
Appendix 3: Randomization Arms	31

Abbreviations and Definitions

- Activities of Daily Living (ADLs)
 - An assessment designed to assess one's ability to complete basic self-care skills.
- Adverse Event (AE)
 - Any untoward medical occurrence associated with or observed in the context of a study procedure. For this study and patient population, an AE will be considered any suicidal ideation. No other events will be considered AEs as this patient population is ill and it is expected that other untoward medical occurrences will occur.
- Clinical Trial Management System (CTMS)
 - For this study, a CTMS known as OnCore will be utilized to manage the study's administrative responsibilities and subject level documentation.
- Duke Regional Hospital (DRH)
 - Study site in which eligible patients will be enrolled.
- Duke University Hospital (DUH)
 - Study site in which eligible patients will be enrolled.
- Oregon Health & Science University (OHSU)
 - Study site in which eligible patients will be enrolled.
- University of Colorado-Denver (COL)
 - Study site in which eligible patients will be enrolled.
- University of Washington-Seattle (UW)
 - Study site in which eligible patients will be enrolled.
- Electronic Data Capture (EDC)
 - For this study, the EDC will be supported and secured by Duke University via REDCap in which relevant study data, such as screening, enrollment, and clinical variables both from research participants' medical records and app will be documented.
- Electronic Health Record (EHR)
 - Used interchangeably with EMR; the EHR is the patient-specific medical record located in the secure MaestroCare (aka: EPIC) or other electronic medical record platform.
- Electronic Medical Record (EMR)

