 - Defined as an adverse event that is both serious and expected in nature; the event may have a reasonable possibility that it is related to a study. SAEs for this study are defined as a suicide attempt, a hospitalization, or death.
- Suicide Ideation (SI)
 - The idea of committing self-harm and/or the intent to act on the idea of committing self-harm.
- Unanticipated Problem (UP)
 - Any other event, not meeting the definition of PD, UP, AE or SAE that, in the opinion of the principal investigator, merits documentation as it occurred outside the expected design of the study and/or study procedures. These events, like PDs, UPs, AEs, or SAEs, may be reported to the IRB and/or the study sponsor, as applicable.

Clinical Protocol Synopsis

1. Title

Optimizing a self-directed mobile mindfulness intervention for improving cardiorespiratory failure survivors' psychological distress (a.k.a., 'LIFT2')

[figure not shown]
2. Background & Rationale

As survival has improved for the 2 million people with cardiorespiratory failure managed annually in the US intensive care units (ICUs), it has become apparent that these patients suffer from severe and persistent post-discharge symptoms of psychological distress including depression, anxiety, and post-traumatic stress disorder (PTSD). However, few targeted interventions exist that are relevant to patients' experiences and that accommodate their many physical, and social barriers to personalized care. To fill this gap, we developed an innovative app-based mobile mindfulness training program that promotes automated care delivery and self-management of symptom-related distress.

Previously, a pilot randomized clinical trial (RCT) called LIFT (R34 AT00819) in which this project is built on, compared mobile mindfulness to both a standard telephone mindfulness program and an ICU education control among survivors of cardiorespiratory failure. LIFT demonstrated that mobile mindfulness was feasibly delivered, acceptable, usable, and had a greater clinical impact on psychological distress than either comparator. This trial also highlighted opportunities to improve the intervention's impact related to its targeted population, content delivery, and system technology.

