If an individual states that they wish to drop out, the study team will respect that as well. A follow-up question may be asked to ascertain the reason for withdraw; however, this is for documentation purposes only. Additionally, the study and/or site PI retain the right with withdraw the participant from the study if they feel that participation is no longer in the participant's best interest and/or the participant is non-compliant despite numerous attempts to contact by the study team.

Vulnerable Populations

This project will not enroll individuals from vulnerable populations (e.g., imprisoned persons, minors).

Adverse events (AEs), serious adverse events, (SAEs) and unanticipated problems (UPs).

It is recognized that there is a slight risk that some participants may become distressed when completing self-report measures or participating in interviews. When necessary, participants who experience psychological distress *related to completing questionnaires* will be referred for appropriate psychiatric or psychological care. All participants will have access to the PI's contact information 24 hours a day (shown in the consent form). If a telephone interview is required, a trained study team member who has been trained to be sensitive to the nature of these issues will conduct it.

It is anticipated, in this study, for AEs to be extremely rare as it is a behavioral study. However, it is possible that participants could become distressed in a hospital setting or post-discharge due to increased illness and/or limitations. As such, participants could exhibit signs of and/or experience suicidal ideations or be admitted for mental health symptoms. Therefore, for this study, only increased levels of distress related to completing the questionnaires or completing the coping skills practice and/or suicidal ideations will be considered AEs.

Like, AEs, it is not anticipated that SAEs will occur. However, for this study, an SAE would be defined as a suicide attempt, a hospitalization (post hospitalization that initiated the patient's eligibility for study participation), or death. All serious adverse events will be reported within the standard timelines required to the IRB, study sponsor, and/or DSMB, as appropriate and when applicable.

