3. Severe: significant symptoms requiring invasive intervention; subject seeks medical attention, needs major assistance with ADL

Reporting Procedures

Adverse and Serious Adverse Events

For symptoms that are either great in total burden (i.e., total score is high), a delegated study team member (e.g., therapist) will call the participant to check in. For specific symptoms such as the suicidal ideation, a delegated study team member will also call the participant and assess the severity of the situation, triaging them as appropriate to psychiatric support.

For other matters, the study team will maintain frequent telephone contact with most participants, and can refer those with concerning symptoms.

All deaths will be reported to NIH Program Officer and to the DSMB Chair within 72 hours of study's knowledge of death. For each patient who dies, a brief report containing the following variables will be provided:

- Age
- Principal diagnosis
- Number of comorbidities
- Admission APACHE II score

- Days since enrollment
- Brief description of circumstances surrounding death including expected or unexpected.

Serious (fatal or life-threatening) SAEs that are unanticipated and that are related to the intervention will be reported to the NHLBI Program Officer and to the DSMB Chair within 7 days of study staff's knowledge of the SAE.

The summary of all other SAEs will be reported to NIH Program Officer and to the DSMB quarterly, unless otherwise requested by the DSMB.

Protocol Deviations and Other Unanticipated Problem Reporting

Incidents or events that meet the reporting criteria, as outlined by the Duke IRB, will be reported to the Duke IRB as needed.

The following will be included, at a minimum:

- A detailed description of the event, incident, experience, or outcome;
- A description of any changes to the protocol or other corrective actions that have been taken or are proposed in response to the unanticipated problem.

Reporting for Multi-Center Trials

The study site must immediately report to the coordinating center and study manager any serious adverse event, whether or not considered study related, including those listed in the protocol and must include an assessment of whether there is a reasonable possibility that the study caused the event within 48 hours of PI awareness of the event.

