The initial DSMB meeting will occur before the initiation of subject enrollment for the purpose of updating members on the study, ensuring agreement on the review process, establishing the review methodology and procedures, ensuring all conflicts of interest are disclosed (to be reviewed by NHLBI staff), reviewing the protocol, and codifying a written charter. The NHLBI's Data Safety Monitoring Plan (DSMP) Template will be used to guide the drafting of the charter. This document will specify procedures for protocol amendments, ensuring participant confidentiality and privacy, ensuring database protection, coordinating center responsibilities, creating adverse outcome definitions (adverse events, unanticipated problems, and serious adverse events), protocol for reporting and responding to adverse events while also maintaining subject confidentiality, justifying sample size, assessing accrual and compliance, halting and stopping rules (drafted with the assistance of the DSMB chair and the DSMB lead statistician), approving informed consent documents, and guidelines for quality control and quality assurance. Before enrollment begins, the DSMB charter will be approved by both the DSMB and the NHLBI; additionally, ClinicalTrials.gov registration will be finalized as per the Milestone Plan shown in the Research Strategy document.

The first DSMB data review will occur either after the first 60 participants have been enrolled or enrollment has occurred for 6 months, whichever is observed first. Thereafter, the DSMB will review cleaned data reports (provided by the Project Manager 2 weeks before the DSMB meeting) every 3 months during enrollment and follow up, and will prepare a report with any recommendations within 2 weeks following their review. The specific study metrics that the DSMB will review at each meeting include enrollment rate, dropout rate, HADS scores, PTSS scores, and Adverse Events. The primary safety measures will be Adverse Events reports and HADS scores.

Other items reviewed by the DSMB at each meeting will include: (a) data quality, completeness, and timeliness; (b) performance of the individual sites; (c) adequacy of compliance with goals for recruitment and

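### The protocol's two closed AE definitions disagree on practice-related distress, and its SAE definition requires expectedness that the reporting rules judge separately

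*Protocol*

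**What the plan says.** **Adverse events.** The Adverse Event entry in the protocol's Abbreviations and Definitions states: "For this study and patient population, an AE will be considered any suicidal ideation". It then closes the list: "No other events will be considered AEs as this patient population is ill". Section 12, under the heading on AEs, SAEs and UPs, has a different list that is also closed: "only increased levels of distress related to completing the questionnaires or completing the coping skills practice and/or suicidal ideations will be considered AEs".

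**Serious adverse events.** The Definitions entry opens with a general sentence, "Defined as an adverse event that is both serious and expected in nature", and ends with a study-specific list: "SAEs for this study are defined as a suicide attempt, a hospitalization, or death". Section 12 names the same three events ("an SAE would be defined as a suicide attempt, a hospitalization" and so on). It excludes the admission that made the patient eligible and sets no expectedness condition.

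**Expectedness and reporting.** Section 12, Expectedness, has the study PI judge each event as expected or unexpected. Section 12, Reporting Procedures, sets a 7-day report for a subset of fatal or life-threatening events: "SAEs that are unanticipated and that are related to the intervention will be reported".

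**Use.** Section 14, on the DSMB, states: "The primary safety measures will be Adverse Events reports and HADS scores". It also lets the DSMB request formal tests of AE rates between factor-based groups. SAP Sections 3.1 to 3.3 list no AE or SAE outcome.

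**The concern.** Each AE definition is worded as complete, and nothing says which one governs. Site staff who follow the Definitions would not enter non-suicidal distress caused by the practice as an AE. Staff who follow Section 12 would.

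This category matters in this trial. Section 12, in the oversight plan for severe psychological distress, says participants will be warned that training can bring up distressing thoughts and feelings. Dose is one of the three randomized factors, and its high level adds meditation sessions (Section 3, Aim 2). Practice-related distress is therefore a harm that could plausibly differ by factor level. The other primary safety measure, HADS, is not among the instruments listed for the trial surveys in Section 3 or Section 7, so the AE count carries more of the safety monitoring than the DSMB section suggests.

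The SAE wording is a separate and smaller fault. If an SAE must be expected, the unanticipated SAE that Reporting Procedures sends by the 7-day route cannot exist under the general sentence.

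**Working it through.** No arithmetic applies: the documents state no AE or SAE rate or count to reproduce. The check is to classify each kind of event under each text.

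| Event | Definitions | Section 12 |
|---|---|---|
| Suicidal ideation | AE | AE |
| Non-suicidal distress from the practice | Not an AE | AE |
| Non-suicidal distress from the questionnaires | Not an AE | AE |
| Suicide attempt, later hospitalization, death | SAE by the list | SAE by the list |
| Unexpected event among those three | SAE by the list, but fails the general sentence | SAE by the list; 7-day report if also fatal or life-threatening and related |

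1. **AE conflict.** Rows 2 and 3 are classified in opposite ways. The Definitions entry cannot be read as shorthand for Section 12, because it expressly rules out everything except suicidal ideation.

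2. **What is lost under the narrower definition.** Section 12 has two AE categories: distress tied to the questionnaires or practice, and suicidal ideation. The first would be recorded as zero. Section 12 also grades severity from mild, with no intervention needed, to severe, and assesses relationship to the intervention. Distress that is not an AE gets neither assessment.

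3. **SAE general sentence.** It sets three conditions: the event is an AE, it is serious, and it is expected. The third conflicts with Expectedness, where this is a separate PI judgement, and with the 7-day route, which presupposes that an SAE can be unanticipated. Section 12 also says SAEs are not anticipated at all. The first condition conflicts with the AE entry: hospitalization and death cannot be AEs there, yet they are listed as SAEs.

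4. **Effect on SAE counts.** Row 4 is the same under both texts, because both lists name the events directly and attach no condition. The fault lies in the general sentence and its fit with the 7-day route. The three named events would still be counted.

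5. **Size.** The nearest figure is in the Suicidality Response Plan: in past studies with over 400 participants, fewer than 5% needed a call from the PI. That describes cases the alert route catches. It says nothing about the milder distress the route would miss, so it cannot size the loss.

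**The case against.** The strongest reply is that the protocol has other routes for distress, and that the conflict matters only where they fail.

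- **A reader might infer that practice-related distress would never reach the DSMB.** The documents do not support that. Section 12 has safety concerns discussed at once with the PI, including severe distress without suicidality, and alert resolutions logged for the DSMB. A high symptom score prompts a call to the participant. The DSMB reviews PTSS scores and dropout. PHQ-9, GAD-7 and PTSS are trial outcomes analysed by factor. These routes do not depend on the AE definition.
- **A reader might infer that AE counts could not be compared by factor level.** That does not follow. Site is a minimization variable (SAP Section 2.4), so a site that under-records should do so about equally at both levels of each factor. The comparison survives with less sensitivity. Nothing shows that sites in fact apply different definitions.
- **A reader might infer that unexpected serious events drop out of the SAE count.** The unconditional lists prevent that for the three named events. All deaths are also reported within 72 hours, and sites must report any SAE whether or not it is thought related.

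These replies narrow the consequence but leave the contradiction in place. A contact-log entry is not an AE with recorded severity and relatedness, and mild or moderate distress may trigger no alert. The UP category rests on the PI's opinion. The DSMB charter is meant to set adverse outcome definitions, but it is not among the documents. It cannot be credited with settling the matter, and divergent practice cannot be asserted either.

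**Conclusion.** The point holds in a limited form. The protocol has two operative AE definitions that cannot both be followed, and they differ on a harm the protocol foresees. Under the narrower one, one of Section 12's two AE categories is empty in a designated primary safety measure. The likely loss is mainly milder practice- or questionnaire-related distress, plus some sensitivity in any AE comparison by factor level that the DSMB requests. The number of events cannot be stated.

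The SAE limb is a defect of definition: *expected* contradicts the Expectedness and Reporting Procedures text but leaves the three named events countable.

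This rests on the protocol text alone and assumes no unseen charter or site manual has already fixed a single definition. It should be corrected because safety reporting depends on it. It has no bearing on the PHQ-9 estimates or the sample size.

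**What to change.** 1. Reconcile the Definitions entry and Section 12 into one AE definition, used in both places and at all sites. Section 12's list is the one that captures the harm the protocol foresees.
2. Delete the words *and expected* from the SAE entry, so that expectedness is judged separately as Section 12 already provides.
3. State in both places that suicide attempt, hospitalization after the index admission, and death are reportable as SAEs whether or not they meet the AE definition.
4. If data collection has ended, report which AE definition each site applied, so that AE counts by factor can be read correctly.

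The cost is protocol wording, a check of the AE form against it, and possibly a few more AE entries. Routine tabulation of AEs and SAEs by factor level is optional, since Section 14 already lets the DSMB ask for such comparisons.

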The overall objective is to optimize the mobile mindfulness training intervention (i.e., mMT) by identifying which components contribute most meaningfully to feasibility, usability, and clinical impact on symptoms of psychological distress assessed over a 3-month follow up period.

We hypothesize that the optimal mMT use case will include the following factor components: high dose, app-based approach to responders, and app-initiated study introduction.

Feasibility will be evaluated by comparing observed to targeted benchmark rates of consent (70%), completion of weekly surveys (75%), and 3-month retention (75%). We will use server analytics to quantify participants' app adherence (e.g., frequency of daily use, average session duration). More specifically, adherence will be monitored closely using the app-integrated data system and automated web analytics. In particular, mobile web app analytics will allow real-time monitoring of each participant's frequency of app use, average duration of app use per session, completion of weekly components, and other behaviors. Weekly reports generated by the study data system will allow the study team to make proactive interventions (e.g., reminder emails and calls) if needed to either get the participant back on schedule or to address a logistical need. Acceptability will be measured with the Client Satisfaction Questionnaire (CSQ; target mean ≥ 10) and by analysis of Aim 3's semi-structured interviews. Usability will be assessed with the Systems Usability Scale (SUS; target mean ≥ 85).

Secondary outcomes will be assessed to ascertain information on the multidimensional effects of the intervention.

- Anxiety symptoms: Generalized Anxiety Disorder 7-item scale (GAD-7).
- Post-traumatic distress disorder (PTSD) symptoms: Post-Traumatic Stress Syndrome Inventory (PTSS).
- Quality of life: The EuroQOL-5D (EQ-5D) and its 100-unit visual analog scale (VAS).
- Physical symptoms: Patient Health Questionnaire 10-item symptoms scale (PHQ-10).

5. Study Population

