- **Post Randomization Failure:** defined as any patient who consents to the study, completes the initial study visit, is discharged to an independent home setting, completes survey T1 and is randomized to the study, and anytime during the first month study participation is re-admitted to the hospital. Should this occur, the patient may be terminated if the hospitalization lasts ≥ 7 days and/or the patient is unwilling or unable to continue study procedures.
 - *Note: If the participant is terminated, he/she will be included in the analyses up to the point that they were excluded.*
- **Withdraw by PI or Self:** defined as any individual who voluntarily consents to participate in the study, but is then withdrawn from the study.
 - The PI may withdraw a participant at any time without their consent if the PI deems it is in their best interest to no longer participate OR the patient demonstrates continuous lack of compliance with study protocol and study procedures.
 - The patient may withdraw themselves at any time; the study team will be asked to document the reason for withdraw for study records.

Patients who reach this status will have no additional follow-ups or study requirements. Patients who are assigned this status must be maintained on the enrollment log. A reason for withdraw should be recorded in the study records.

- **Lost to Follow-Up (LTF):** defined as any individual who voluntarily consents to participate in the study but after non-compliance and at least 3 documented, attempted contacts appropriately spaced 1-5 days apart, the individual will be considered LTF.
 - For aim 2 only:
 - Patients who reach this status will have no additional follow-ups or study requirements. Patients who are assigned this status must be maintained on the enrollment log.
 - A patient who returns the study team's contacts within 1 week of last attempted contact may resume study participation.
- **Completed:** defined as any individual who both consented and randomized to the study and completed T1-T3 (aim 2 only) or any individual who completed assigned study visit (aims 1, 3 and 4). Individuals who reach this status have no additional follow-up or study requirements. Individuals who are assigned this status must be maintained on the enrollment log.

Study Visits

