Given the nature of this study, it is anticipated that most enrolled patients will not complete their study visits within the assigned protocol window. Additionally, it is expected that visits and/or mMTpractices will be missed. As such, these will not be considered protocol deviations. Should other protocol deviations or unanticipated problems occur, they will be discussed with the PI, documented, and reported to the IRB, study sponsor, and/or DSMB, as appropriate and when applicable.

Period and Frequency for Event Assessment and Follow-Up

Protocol deviations and other unanticipated problems, as well as AEs and SAEs, will be recorded in the data collection system throughout the study and reported, as appropriate, to the IRB, study sponsor, and/or DSMB, when applicable.

The study team will record all reportable events with start dates occurring any time after informed consent is obtained until 7 (for non-serious AEs) or 30 days (for SAEs) after the last day of study participation. At each study visit, the study team will inquire by way of verbal or written request and/or EMR review, of the occurrence of AE/SAEs since the last visit. Events will be followed for outcome information until resolution or stabilization.

Characteristics of an Adverse or Serious Adverse Event

Relationship to Study Intervention

To assess relationship of an event to study intervention, the following guidelines are used:

1. Related (Possible, Probable, Definite)
 - a. The event is known to occur with the study intervention.
 - b. There is a temporal relationship between the intervention and event onset.
 - c. The event abates when the intervention is discontinued.
 - d. The event reappears upon a re-challenge with the intervention.
2. Not Related (Unlikely, Not Related)
 - a. There is no temporal relationship between the intervention and event onset.
 - b. An alternate etiology has been established.

Expectedness

The Study PI will be responsible for determining whether an event is expected or unexpected. An event will be considered unexpected if the nature, severity, or frequency of the event is not consistent with the risk information previously described for the intervention.

Severity

The following scale will be used to grade adverse events:

1. Mild: no intervention required; no impact on activities of daily living (ADL)
2. Moderate: minimal, local, or non-invasive intervention indicated; moderate impact on ADL

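### T2/T3 outcome collection stops for randomized participants withdrawn for non-compliance or declared lost to follow-up, and no analysis tests departures from missing at random

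*Protocol*

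**What the plan says.** Protocol section 7 defines two statuses that matter here.

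- **Withdraw by PI or Self.** The PI may withdraw a participant without the participant's consent, for best-interest reasons or because "the patient demonstrates continuous lack of compliance with study protocol and study procedures". Section 12 (Withdraw While in Study) restates the second ground as applying when "the participant is non-compliant despite numerous attempts to contact by the study team".
- **Lost to Follow-Up.** In the protocol's words, "after non-compliance and at least 3 documented, attempted contacts appropriately spaced 1-5 days apart, the individual will be considered LTF". For Aim 2, someone who responds "within 1 week of last attempted contact may resume study participation".

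The same sentence stands under both: "Patients who reach this status will have no additional follow-ups or study requirements".

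Protocol section 9 and SAP section 4 both describe the analysis as intention-to-treat. SAP section 4 expects at most 20% missing outcomes, fits a likelihood model valid under MAR, compares baseline characteristics of completers and non-completers, and adjusts for covariates that predict missingness as a sensitivity analysis. It acknowledges that dropout may differ by condition, but only in discussing correlation between effect estimates.

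Some safeguards exist. Weekly reports let staff "make proactive interventions (e.g., reminder emails and calls) if needed to either get the participant back on schedule" (Protocol section 4). Protocol section 14 says the "metrics that the DSMB will review at each meeting include enrollment rate, dropout rate", and it allows protocol changes if dropout differs. Section 12 also says "it is expected that visits and/or mMTpractices will be missed", so a single missed check-in is not shown to start the LTF process.

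**The concern.** Adherence is measured after randomization, and two of the three factors compare therapist contact with the app, so contact and engagement could differ by factor level. Stopping outcome collection because of non-compliance can therefore remove T2 and T3 scores unequally across the levels being compared. Component choices rest on the T2 PHQ-9 effects and may be reconsidered on T3 (SAP section 4).

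A bias needs two things: loss must differ by level, and the lost participants' scores must differ from what T1 and the covariates predict. The documents do not show that either will happen. The direction is also unknown, since people may stop because they feel better. But the plan neither collects the values that could still be obtained nor examines the effect of those that cannot.

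**Working it through.** **1. Reproducing the plan's power figure.** SAP Appendix B gives Var(T1) = 27.95, Var(T2) = 19.28 and Cov(T1,T2) = 9.67, with N = 192 at T2.

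- Residual variance of T2 given T1: 19.28 − 9.67²/27.95 = 15.934 (SD 3.992).
- SE of a main effect: 2 × √(15.934/192) = 0.576.
- Power for 1.6 points, two-sided 0.05: 79.3%, against 79.8% in SAP Table 2. The other rows agree within 2 percentage points.

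The power figures are sound, and the same SE is the yardstick below. The decision rule is 1.6 points or p < 0.05, and p < 0.05 is reached at 1.96 × 0.576 = 1.13 points.

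**2. When LTF becomes final.** Three attempts 1-5 days apart put the last one 2-10 days after the first. Adding 7 days for return gives 9-17 days. The documents do not say what starts the attempts, so the start days are assumptions.

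- Start on day 8: final on day 17-25, before T2 at day 30. This leaves 60 − 25 = 35 to 60 − 17 = 43 days of the SAP's T2 window (day 60, SAP section 2.6).
- Start on day 31, after a missed T2: final on day 40-48, with 12-20 days of that window left and T3 (day 90) still ahead.
- LTF can be final before day 30 if attempts start by day 20 (1-day spacing: 20 + 9 = 29) or day 12 (5-day spacing: 12 + 17 = 29).

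**3. Possible bias (all inputs hypothetical).** In each level let q be the share non-compliant and w the share lost, all of them non-compliers. Let d be the non-complier minus complier difference at T2 given T1. The true level mean is shifted by dq and the observed mean by d(q − w)/(1 − w), so the observed mean is too low by d·w(1 − q)/(1 − w). For the effect B minus A:

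bias = d × [w_A(1 − q_A)/(1 − w_A) − w_B(1 − q_B)/(1 − w_B)]

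Take w_A = 0.05 and w_B = 0.15.

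- q = 0.30 in both: 0.05 × 0.70/0.95 − 0.15 × 0.70/0.85 = −0.0867.
- q = 0.20 and 0.40: 0.05 × 0.80/0.95 − 0.15 × 0.60/0.85 = −0.0638.

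If a share r of the lost answer, w becomes w(1 − r).

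| q (A / B) | d | Total bias | Left if r = 0.25 | Left if r = 0.50 |
|---|---|---|---|---|
| 30% / 30% | 3 | −0.260 | −0.184 | −0.116 |
| 30% / 30% | 5 | −0.433 | −0.307 | −0.194 |
| 20% / 40% | 3 | −0.191 | −0.135 | −0.084 |
| 20% / 40% | 5 | −0.319 | −0.224 | −0.141 |

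The negative sign means the level with more loss looks better. It reverses if non-compliers score better than compliers. By subtraction, continued collection removes 0.06-0.13 points (0.10-0.22 SE) at r = 0.25 and 0.11-0.24 points (0.19-0.42 SE) at r = 0.50. A simulation of 4,000 trials of 240 per case agreed within about two Monte Carlo SEs (for r = 0: −0.262, −0.438, −0.193, −0.311; Monte Carlo SE 0.009-0.010).

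**4. What stays missing.** At 20% missing, each 1-point shift (delta) applied to one level only moves a main effect by 0.20 × 1 = 0.20 points. One SE therefore needs 0.576/0.20 = 2.9 points.

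**5. Yield.** With 120 per level, 5% and 15% are 6 + 18 = 24 people. If 25-50% answer, that gives 6-12 more T2 values.

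**The case against.** The strongest reply is about materiality. PI withdrawal is discretionary, LTF requires unanswered contacts as well as non-compliance, and low users who respond stay in. The groups are therefore mostly non-responders, for whom a 25-50% response may be optimistic. The illustration assigns 24 of the 240 − 192 = 48 planned losses to these groups, although death, self-withdrawal and readmission also contribute. No document supplies the loss split or the score difference. The day-8 timing rests on an unstated trigger.

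Participants are still analysed as randomized, and T1 stays in the likelihood. Dropout explained by the factors, T1 PHQ-9 or the minimization variables is MAR. This is also a screening experiment ahead of a definitive trial, and its choices may be revisited on other evidence.

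Most of this stands and limits the point: a large bias is not shown. It does not remove the gap. Reminders act before the status is assigned, and DSMB review of dropout recovers no PHQ-9 value. Neither they nor covariate adjustment tests a departure from MAR. The timing point also survives in its most conservative case, because LTF after a missed T2 still closes inside the T2 window and well before T3.

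Two practical objections also stand. Surveys that contain the suicidality item would go to people who have not been answering contacts, so staff must be able to handle alerts. And the collection change may come too late: the SAP log runs to November 2023 and SAP section 2.6 refers to the final dataset, though no last-visit date is given.

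**Conclusion.** The point holds as a worthwhile, inexpensive improvement, with medium confidence. The protocol states a rule that gives up T2 and T3 outcomes that might still be obtained from two groups defined by post-randomization behaviour, and the SAP has no analysis outside MAR. Under the assumed inputs the total bias is at most 0.43 points, about three quarters of an SE, and continued collection could remove at most 0.24. All of this depends on unequal loss or non-compliance by level and on a residual score difference that the documents do not give. The case for change rests on its low cost, not on a large expected bias.

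**What to change.** **Protocol.** State that non-compliance or unanswered contacts alone do not end outcome collection. For PI withdrawal for non-compliance and for LTF only, keep sending the existing T2 and T3 app surveys unless the participant has withdrawn consent for follow-up, and assign final LTF only after the T3 window closes. Include the values obtained in the intention-to-treat model. Explicitly exclude participants withdrawn for clinical, safety or best-interest reasons, whose handling stays as written. Self-withdrawal, termination after readmission and the rules for ending intervention contact are also unchanged.

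**SAP.** Tabulate missingness and its reasons by level of each factor. Add a delta-adjusted sensitivity analysis for data missing not at random, with delta varied by level and in both directions, and report whether any component decision changes.

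**Cost.** Protocol wording, two existing surveys with reminders for a minority of participants, one table and one sensitivity analysis. The downsides are low yield from some non-responders, extra reminder effort, and handling of survey-triggered alerts by existing staff. For participants already past T3 only the SAP part applies, and it needs no new data.
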